What is the analgesic effect of peribulbar anesthesia compared to topical anesthesia in patients with diabetic retinopathy undergoing PRP with argon laser?

Objectives and hypotheses

General objective

To determine the reduction in the NRS scale between eyes of patients undergoing PRP following an injection of peribulbar anesthesia with 2% lidocaine + 0.5% bupivacaine versus those eyes receiving a sham injection.

Specific objectives

- To determine the pain score using the NRS scale between the eyes of patients undergoing PRP following the application of a sham injection vs transeptal anesthesia with 2% lidocaine + 0.5% bupivacaine.
- To measure and compare the frequency of adverse effects and complications associated with the transeptal anesthesia intervention versus those of patients receiving a sham injection.
- To measure heart rate before and after the application of panretinal photocoagulation.
- To measure respiratory rate before and after the application of panretinal photocoagulation.

-
- To measure systolic and diastolic blood pressure pre- and post-application of panretinal photocoagulation.
- To measure oxygen saturation pre- and post-application of panretinal photocoagulation.

General hypothesis

In patients who received panretinal photocoagulation, eyes undergoing peribulbar anesthesia will present a lower pain score on the NRS scale than eyes that received a sham injection.

Specific hypotheses

- In patients who received panretinal photocoagulation, eyes undergoing peribulbar anesthesia will present a pain score on the NRS scale 20% lower than eyes that only received a sham injection.
- The incidence of adverse effects and complications of peribulbar anesthesia is similar to that of the sham injection.
- In eyes undergoing intervention with prior peribulbar anesthesia, the post-procedure increase in heart rate will be 10% lower than the increase observed in eyes receiving a sham injection.
- In eyes undergoing intervention with prior peribulbar anesthesia, the post-procedure increase in respiratory rate will be 10% lower than the increase observed in eyes receiving a sham injection.

- In eyes undergoing intervention with prior peribulbar anesthesia, the post-procedure increase in systolic and diastolic blood pressure will be 10% lower than the increase observed in eyes receiving a sham injection.

Methods

Study design

Prospective, randomized, single-masked, controlled trial

Patients

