Patients were recruited from the Asociación Para Evitar la Ceguera en México, I.A.P. Retina department according to specific eligibility criteria. Adults aged 18 years or older with proliferative diabetic retinopathy who were scheduled to undergo their first PRP session and were able to maintain the required posture at the slit lamp throughout the procedure were included. Exclusion criteria were a history of phobic anxiety disorder related to needles or injections; known allergies or hypersensitivity to lidocaine, bupivacaine, or tetracaine; use of analgesics within 24 hours prior to treatment; and cognitive or motor impairments that could hinder effective communication of pain.

Study design

A block randomization scheme was created to ensure a balanced allocation of the eyes across the study groups. Eleven blocks containing four possible permutations for the two groups were created. The intervention group received peribulbar anesthesia and the control group received topical anesthesia. The blocks were numbered randomly from one to 11, and one eye of each participant was assigned to the treatment or control group according to the permutation, with the contralateral eye assigned to the corresponding alternative.

The eyes assigned to the treatment group received a single drop of topical 5% tetracaine to improve patient comfort during the peribulbar injection, followed by a two-minute observation period. A mixture of 1.5 mL of 0.5% bupivacaine and 1.5 mL of 2% lidocaine was prepared in a 3 mL syringe. The peribulbar injection was administered using a 25G needle inserted horizontally through the inferior palpebral conjunctiva, directed axially over the infraorbital rim, and then angled upward to deliver the anesthetic into the orbit.

After a five-minute latency period, the eyes assigned to the control group, which also received 5% tetracaine, were administered a sham injection. In this group, topical 5% tetracaine was applied, followed by a two-minute observation period. The sham injection consisted of a 3 mL syringe filled with normal saline, without a needle, used to simulate insertion by applying pressure at the same site as the peribulbar injection.

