Five minutes after the sham injection, the participants underwent PRP using a double-frequency Nd:YAG 532-nm laser (PUREPOINT®, ALCON) following the standard PRP protocol, starting with the right eye. Each eye received between 1,200 and 1,500 burns, with sizes ranging from 200 μ m to 500 μ m. Pulse durations were set between 100-200 ms. The power was titrated before initiating treatment to obtain a gray-whitish burn, and adjusted throughout the procedure in order to avoid under- or over-treatment. A period of 10 minutes was provided between the right- and left-eye PRP sessions.

Variables and Measurements

The primary variable assessed in this study was patient perception of pain during PRP administration in each eye, measured using the numerical rating scale (NRS). The Initiative on Methods, Measurement, and Pain Assessment in Clinical Trials (IMMPACT) recommends the use of this scale due to its simplicity, patient preference, and high completion rates, especially among elderly individuals. The NRS measures pain intensity on a scale of 0 to 10, where 0 corresponds to the absence of pain and 10 represents the

worst pain imaginable.²⁴ The evaluator administering the NRS was not masked to the treatment allocation. The secondary variables assessed in this study were heart rate, respiratory rate, oxygen saturation (SpO₂), and blood pressure measured before and after the application of PRP in each eye. All vital signs were measured with the Aquarius Vital Sign Monitor (Shenzhen Northern Meditec Limited, Shenzhen, China) at baseline before the start of PRP, and at the 1-, 5-, 10-, and 15-minute marks while undergoing PRP application in each eye.

Safety was evaluated by monitoring for ocular and non-ocular adverse events, assessing extraocular movements after peribulbar injection, and conducting a 45-minute observation period after the PRP session.

Standardized methods

A) Topical anesthesia with 0.5% Tetracaine

1. Patient seated in a comfortable position.
2. 1 drop of 0.5% tetracaine will be applied onto the ocular surface to be treated and the conjunctival fornices.
3. Any excess residue will be cleaned with a cotton swab.

B) Peribulbar injection of 3 mL of 2% lidocaine + 0.5% bupivacaine

1. Patient in a comfortable position.
2. 2 drops of 0.5% tetracaine will be applied to the conjunctival fornices 10 minutes prior to the administration of anesthesia.

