presented as mean (SD), and data from non-normally distributed variables as median (IQR). The grouped quantitative variables had a normal distribution; however, when the treatment groups were separated, all the variables had a non-normal distribution. Repeated measurements of related groups with a non-normal distribution were analyzed using the Friedman test. Group comparisons of unrelated groups with a non-normal distribution were performed using the Mann-Whitney U test. The measurements of vital signs, NRS score, and laser parameters were registered into a coded Excel spreadsheet (Microsoft Corporation), and statistical analysis was performed using SPSS software (version 29.0, IBM, Chicago, IL, USA). A p-value of < 0.05 was considered statistically significant.

References

6. GBD 2019 Blindness and Vision Impairment Collaborators. Causes of blindness and vision impairment in 2020 and trends over 30 years, and prevalence of avoidable blindness in relation to VISION 2020: the Right to Sight: an analysis for the Global Burden of Disease Study. *Lancet Glob Health.* 2021;9(2):e144-e160. doi:10.1016/S2214-109X(20)30489-7

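### The vital-sign analysis uses neither the pairing of eyes nor adjustment for the baselines collected; a paired, baseline-adjusted contrast would be more precise, with carry-over as its one real cost

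*Combined protocol and SAP*

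**What the plan says.** **Hypotheses.** Under Specific hypotheses, the heart-rate prediction is that "the post-procedure increase in heart rate will be 10% lower than the increase observed in eyes receiving a sham injection". Respiratory rate and systolic and diastolic blood pressure are worded the same way.

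**Allocation.** Under Methods, Study design: "one eye of each participant was assigned to the treatment or control group according to the permutation, with the contralateral eye assigned" to the other arm. Every patient is therefore their own control.

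**Measurement.** Under Variables and Measurements, vital signs are "measured before and after the application of PRP in each eye", and more specifically "at baseline before the start of PRP, and at the 1-, 5-, 10-, and 15-minute marks while undergoing PRP application in each eye". The first phrase points to a separate baseline for each eye. The second can also be read as a single baseline before any laser.

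**Timing.** The laser starts with the right eye: "Five minutes after the sham injection, the participants underwent PRP". Then "A period of 10 minutes was provided between the right- and left-eye PRP sessions".

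**Analysis.** The Statistical Analysis Plan has two relevant sentences: "Repeated measurements of related groups with a non-normal distribution were analyzed using the Friedman test", and "Group comparisons of unrelated groups with a non-normal distribution were performed using the Mann-Whitney U test". It names no paired between-eye test and no covariate. It does not say which vital-sign quantity (level, increase, or which minute) goes into either test.

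**The concern.** The design provides two things that the analysis plan does not use: the pairing of eyes within a patient, and a pre-laser reading that could serve as a covariate. The hypotheses rely on the raw increase. That handles the patient's level in an unpaired test, but it is inefficient once the eyes are compared within patient, because each baseline is a single reading with its own random error and is subtracted with a fixed weight of 1.

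The protocol presents vital signs as the objective complement to a subjective pain score, and it says the evaluator who administered that score was not masked. The hypothesised difference is a tenth of an increase, which is likely to be small. A contrast noisier than it needs to be makes a real difference easier to miss, and a null result could then be read as no objective analgesic effect.

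**Working it through.** **The plan's own figure.** The minimum of 44 patients cannot be reproduced, because no difference or SD is given. Back-solving a two-sided two-sample t-test at 80% power gives a standardised difference of 0.597 with 44 per group, or 0.845 with 22 per group. The documents do not tie 44 to any vital sign, so below it serves only as the number of pairs.

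**Inputs.**
- From the documents: 44 patients, two eyes each, alpha 0.05.
- Assumed, since the documents give no vital-sign variability: equal residual SD s for baseline B and during-laser level D after removing the patient effect; their correlation r within an eye; s = 6 and a true between-eye difference of 3 units for illustration.

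**Step 1. Under the named unpaired test, the increase helps.** Per eye, the variance of the increase relative to the raw level is 2(1 − ρ), where ρ is the total baseline-to-laser correlation including the patient effect. At an assumed ρ = 0.8 this is 0.40. In a simulation of 44 patients (assumed patient SD 10, error SD 4, per-eye session SD 0 to 6, effect 3), Mann-Whitney had power 0.06 to 0.09 on raw levels and 0.65 to 0.68 on the increase.

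**Step 2. Under a paired contrast, the patient's level has already gone.**
- Raw increase: Var[(D1 − B1) − (D2 − B2)] = 4s²(1 − r).
- Adjusted for the baseline difference: 2s²(1 − r²), times about 1.025 for one estimated slope at n = 44.
- Ratio before the slope cost: (1 + r)/2, so the reduction is (1 − r)/2.
- Baseline ignored altogether: 2s². The raw increase is worse than this only when r < 0.5.

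SE is the square root of variance/44. Power is from the noncentral t (42 and 41 df).

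| r | reduction | after slope cost | SE raw | SE adjusted | power raw | power adjusted |
|---|---|---|---|---|---|---|
| 0 | 50% | 49% | 1.81 | 1.30 | 37% | 62% |
| 0.3 | 35% | 33% | 1.51 | 1.24 | 49% | 66% |
| 0.5 | 25% | 23% | 1.28 | 1.12 | 63% | 74% |
| 0.7 | 15% | 13% | 0.99 | 0.92 | 84% | 89% |
| 0.9 | 5% | 3% | 0.57 | 0.57 | >99% | >99% |

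Simulated power at r = 0 to 0.7 agrees with these figures to within about 2 points.

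**Step 3. Carry-over into the second baseline.** Let δ be the extra shift in the second eye's baseline after a sham first eye compared with a peribulbar first eye, p the fraction of it still present during the second laser, and b the fitted baseline slope (equal to r here). With the two orders balanced, the size of the bias is (1 − p)δ/2 for the raw increase and |p − b|δ/2 for the adjusted contrast. Take δ = 3 (4 units after sham, 1 after peribulbar; assumed):
- Shift gone (p = 0): raw 1.50; adjusted 0.45, 0.75 and 1.05 at r = 0.3, 0.5 and 0.7. Both exaggerate the benefit.
- Shift fully present (p = 1): raw 0; adjusted 1.05, 0.75 and 0.45. The adjusted estimate understates the benefit.

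Adjustment is the less biased of the two when p < (1 + b)/2.

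**Step 4. Bias and variance together, at r = 0.5.** RMSE = √(SE² + bias²).
- p = 0: raw √(1.28² + 1.5²) = 1.97; adjusted √(1.12² + 0.75²) = 1.35.
- p = 0.5: raw √(1.28² + 0.75²) = 1.48; adjusted 1.12.
- p = 1: raw 1.28; adjusted 1.35.
- p = 1 with δ = 1: raw 1.28; adjusted √(1.12² + 0.25²) = 1.15.

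In these settings adjustment loses only when the carry-over is both large and fully persistent.

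**The case against.** The strongest objection is that the raw increase does no harm in the analysis as written. The only between-group test named treats the eyes as unrelated, and there the increase is what removes the patient's level (step 1). This stands. A reader might infer that the increase damages the planned test; the documents do not support that. The inefficiency appears once the eyes are compared within patient, so adjustment has to come together with a paired analysis.

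Second, a reader might infer that adjustment is free, or that carry-over is itself an argument for it. Neither holds. The second eye's baseline comes after the first eye's laser, so it is not an ordinary pre-treatment covariate, and a fully persistent shift attenuates the adjusted estimate while leaving the raw increase unbiased. The documents do not say which pattern applies. But the raw increase uses the same reading at full weight, so it escapes the problem only when the shift persists completely.

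Third, the gain may be small. A 3-unit difference is 10% of an increase only if the sham increase is 30 units. If it were 10 units (assumed), the target is 1 unit, and with s = 6 power moves from 8% to 12% at r = 0, 12% to 14% at r = 0.5 and 17% to 18% at r = 0.7. Adjustment does not rescue a comparison that small.

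Fourth, a single baseline shared by both eyes would cancel exactly and add no noise. The protocol's wording favours separate baselines but does not settle it. Finally, the 10% hypothesis is a ratio to the sham increase, which an adjusted difference alone does not estimate.

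**Conclusion.** The point holds as a low-cost improvement. The plan specifies neither a within-patient comparison of the vital signs nor use of the baselines as covariates. In a paired contrast, adjusting for the baseline difference reduces variance by about 50% at r = 0, 25% at r = 0.5 and 15% at r = 0.7, with almost no gain above r = 0.9. The direction is secure except at very high r; the size is not, because the documents give no vital-sign SD, correlation or expected increase.

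The conclusion assumes a separate pre-laser baseline for each eye and similar SDs for the two readings. It does not show that the planned test is invalidated by using the increase, that adjustment is without cost, or that a null vital-sign result would be due to this choice. The analysis plan does not even say that the increase is the tested variable. Carry-over from the first eye is a genuine downside, to be checked rather than assumed away.

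**What to change.** 1. For each vital sign, define the outcome as the during-laser level, stating which minute or summary of minutes is used.
2. Analyse the within-patient sham-minus-peribulbar difference in that level, with eye order and the difference in pre-laser baselines as covariates, or use the equivalent mixed model with patient as a random effect. Check the distribution of the paired differences, not of each arm separately.
3. State that each eye has its own pre-laser baseline, if that is so, and when it was read relative to the injections. If one baseline served both eyes, the baseline covariate drops out and only the pairing matters.
4. Report the raw increase per eye alongside, so that the 10% ratio can still be described, and reword the hypotheses to match the adjusted contrast.
5. As sensitivity checks for carry-over, report the paired contrast of raw increases and a comparison restricted to the first-treated eye. The latter is between patients, at most 22 against 22 if order is balanced, so it will be imprecise.

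The cost is wording in the hypotheses and analysis plan, one extra model parameter (about 2.5% in variance) and a result slightly less direct than a simple increase. No new data are needed. The plan is written in the past tense and already reports distributions by treatment group, so if outcomes have been examined, the change should be labelled post hoc.

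### Right eye always lasered first: the allocation randomizes two laser sequences, but no planned test has an order term, which costs power if first and second eyes differ

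*Combined protocol and SAP*

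**What the plan says.** Under Methods, Study design, one eye of each patient is randomized, "with the contralateral eye assigned to the corresponding alternative". On blocking the text says "Eleven blocks containing four possible permutations for the two groups were created". Laser is then given "following the standard PRP protocol, starting with the right eye", and "A period of 10 minutes was provided between the right- and left-eye PRP sessions". The block and the sham are both given before any laser starts.

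The Statistical Analysis Plan names two comparative tests: "Repeated measurements of related groups with a non-normal distribution were analyzed using the Friedman test" and "Group comparisons of unrelated groups with a non-normal distribution were performed using the Mann-Whitney U test". It does not say which is used for the NRS. It names no term for order, side or sequence. The sample size comes from a two-sample t-test.

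**The concern.** Side and laser position coincide: right is first, left is second. Randomizing the treated eye therefore creates two sequences, peribulbar first or sham first, as in a two-period crossover.

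An order effect is plausible. Eligible patients are having their first panretinal session, and the second eye is rated by someone who has just had a full session in the other eye. If a vital-sign baseline is taken before each eye, the second one also follows a full laser session.

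If pain shifts from first to second eye, within-patient differences move up in one sequence and down in the other. An analysis without a sequence term counts that systematic spread as random error. At stake is power for the primary comparison, and in the same way for the vital-sign hypotheses.

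**Working it through.** **The plan's own figure.** The minimum of 44 patients cannot be reproduced, because no mean difference or SD is stated. With two-sided 0.05 and 80% power, it corresponds to a standardized difference of about 0.60 if 44 is the number per arm, or about 0.85 to 0.87 if it is 22 per arm. The check below needs only N = 44.

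**Inputs.** From the documents: 44 patients, right eye first, fellow eye in the other arm. Assumed: 22 patients per sequence (the counts are not stated), SD of within-patient differences 2.5, true difference 1.1 NRS points, order effect p (second eye minus first) of 0, 1 or 2 points. For Mann-Whitney, between-eye correlation 0.5, which makes the per-eye SD 2.5 as well, since 2 × 2.5² × (1 − 0.5) = 6.25.

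**Model.** Let D be sham minus peribulbar, and d1 and d2 the pain reductions when the blocked eye is lasered first and second.
- Right eye treated: mean D = d1 + p.
- Left eye treated: mean D = d2 − p.
- Average of the two: (d1 + d2)/2. The order effect cancels.
- Gap between the two: 2p + (d1 − d2).

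**Precision of the estimate.** With 22 per sequence, the true SE is 2.5/√44 = 0.377 whatever p is. The unadjusted paired analysis instead estimates a variance of about 6.25 + (44/43)p²:
- p = 0: √(6.25/44) = 0.377
- p = 1: √(7.27/44) = 0.407
- p = 2: √(10.34/44) = 0.485

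**Power, unadjusted paired t-test.** This is approximately Φ[(1.1 − 2.017 × estimated SE)/0.377]:
- p = 0: Φ(0.90) = 0.82
- p = 1: Φ(0.74) = 0.77
- p = 2: Φ(0.32) = 0.63

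Simulation agrees to within a hundredth or two:

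| Analysis | p = 0 | p = 1 | p = 2 |
|---|---|---|---|
| Paired t, no order term | 0.82 | 0.77 | 0.64 |
| Order-adjusted | 0.82 | 0.82 | 0.82 |
| Mann-Whitney on eyes | 0.51 | 0.49 | 0.43 |

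With no treatment effect, the simulated type I error of the unadjusted paired test falls to 0.034 at p = 1 and 0.013 at p = 2. The adjusted test stays near 0.05.

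**Loss from ignoring pairing.** At correlation 0.5 and no order effect, the SE that Mann-Whitney in effect assumes is about √2 = 1.41 times the paired one. That explains 0.51 against 0.82 in the first column.

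**Bias if sequences are unequal.** Without an order term, the bias is p × (n1 − n2)/N. For a 24/20 split and p = 1 this is 4/44 = 0.09 points.

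**Drop-to-laser interval for the control eye.** Study design gives two minutes from drop to sham and five from sham to laser, so 7 minutes if the control eye is the right eye. The sham steps under Standardized methods put the drops 10 minutes before the injection, giving 10 + 5 = 15. If the control eye is the left, either figure grows by the first session plus 10 minutes. No session length is stated.

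**The case against.** The strongest reply is that nothing here threatens a positive result. With balanced sequences, which blocking aims for, order cancels from the estimate and the unadjusted test is conservative. The loss is zero if there is no order effect, and the documents give no reason to pick any particular size. The power figures for the paired t-test describe a test the plan does not name. For Mann-Whitney, if that is what is used, a 1-point order effect costs almost nothing and ignored pairing is the larger loss. All of this stands. It limits the point to power and makes keeping the pairing the first priority.

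Three stronger readings are tempting, and the documents do not support them.

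- A reader might infer that order makes the estimate noisier, as if patients were lost: 7.25/6.25 = 1.16, or 44 × (1 − 6.25/7.25) = 6.1 patients, at a 1-point order effect. With balanced sequences the true SE does not change; only its estimate is too large.
- A reader might expect separate results for right-treated and left-treated patients to reveal a sequence-dependent treatment effect. They cannot. With a constant effect of 1.1 and p = 1, the two strata average 2.1 and 0.1; with p = 2, they average 3.1 and −0.9. The gap mixes twice the order effect with any real difference.
- A reader might state the control drop-to-laser interval as 7 minutes for a right eye and at least 32 for a left. That uses one of two conflicting drop timings and infers a 15-minute session from the vital-sign schedule. Only the difference, first session plus 10 minutes, follows from the text.

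**Conclusion.** The point holds as a conditional loss of power. The design randomizes sequence, and the named tests do not use it. Under the stated assumptions, a 1-point order effect lowers paired power from about 0.82 to 0.77 and a 2-point effect to about 0.64; adjustment restores about 0.82. If Mann-Whitney is applied to fellow eyes for the NRS, power is about 0.51 even without an order effect. Bias arises only with unequal sequences and is small in the example shown.

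The SD, the true difference, the order effect, the correlation and the 22/22 split are all assumptions. Order and eye side cannot be separated, but one term absorbs both. An additive order term does not detect or remove a treatment effect that differs by laser position; the intercept then estimates the average over the two positions.

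**What to change.** Analyse the NRS as the within-patient difference, sham minus peribulbar, regressed on sequence coded ±0.5. Report the intercept, with its confidence interval, as the treatment effect. If a rank test is preferred, apply Mann-Whitney to the first-minus-second-eye difference between the two sequence groups. Both keep the pairing and remove a common order effect. In a related simulation (44 patients, difference 0.4 SD, correlation 0.5) the rank version had power of about 0.68 to 0.70, against 0.70 to 0.71 for the regression.

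Use the same order term for the vital signs, and say whether a baseline was taken before each eye. State the number of patients in each sequence. Do not present right-treated and left-treated effects as evidence of a sequence-dependent effect. Reconcile the drop timings in Study design and Standardized methods so that the intervals can be stated.

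The cost is one degree of freedom and some wording; the treated side follows from the allocation. The plan reports its normality results in the past tense, so if the analysis is complete, add this as a labelled sensitivity analysis.

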Among invasive anesthesia techniques, retrobulbar blocks are highly effective due to their rapid onset and complete akinesia and analgesia,^{24,25} but they carry risks such as retrobulbar hemorrhage, optic nerve injury, and cardiorespiratory complications.^{24,26} Peribulbar anesthesia offers similar efficacy by leveraging communication between the extraconal and intraconal spaces while reducing the risk of serious complications such as globe perforation.²⁷ Our anesthetic approach combines short-acting lidocaine with long-acting bupivacaine, optimizing both rapid onset and prolonged analgesia.²⁵ Although many studies have evaluated less invasive strategies such as topical or oral analgesics, their effectiveness in PRP pain management has been limited. A meta-analysis by Arruda et al.²¹ of 15 randomized controlled trials and four crossover trials found that only peribulbar 2% lidocaine significantly reduced pain compared with placebo. Other interventions, including NSAIDs, topical anesthetics, pregabalin, opioids, and acetaminophen, did not yield statistically significant results. Additional studies comparing peribulbar anesthesia with topical agents confirmed superior pain control, particularly during the PRP session, though not at the 48-hour follow-up.²⁸ Subconjunctival lidocaine has also demonstrated efficacy in lowering pain scores, reducing session duration, and increasing the number of laser burns applied.^{22,23} However, more research is needed to compare this technique to peribulbar anesthesia directly.

Despite supporting evidence for several anesthetic approaches, the pain measurements in these studies were predominantly subjective. Pain perception is influenced by various factors—genetic, psychological, cultural, and social²⁹—making objective indicators a valuable complement. Sympathetic responses to pain, such as changes in heart rate, respiratory rate, blood pressure, and oxygen saturation, provide measurable markers.³⁰ Wu et al.¹⁷ compared different anesthetic techniques and found that only peribulbar 2% lidocaine significantly lowered pain scores compared with the control group.

This study aimed to evaluate the efficacy of peribulbar anesthesia using 2% lidocaine and 0.5% bupivacaine compared with topical 5% tetracaine in reducing pain during laser PRP in patients with PDR, using pain rating as a subjective parameter and vital signs as objective parameters.

Research question

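### The vital-sign hypotheses compare the rise between arms, but the SAP specifies no paired analysis of that difference and does not define the post-procedure value

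*Combined protocol and SAP*

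**What the plan says.** **Hypotheses.** Under Specific hypotheses, the heart-rate statement is that "the post-procedure increase in heart rate will be 10% lower than the increase observed in eyes receiving a sham injection". The respiratory-rate and blood-pressure hypotheses have the same form. Oxygen saturation has an objective but no hypothesis.

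**Objectives.** These are more modest and do not compare arms, for example "To measure heart rate before and after the application of panretinal photocoagulation".

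**Measurement.** Variables and Measurements describes the vital signs, ending with "blood pressure measured before and after the application of PRP in each eye". The next sentence but one to concern vital signs gives the timed schedule: "at baseline before the start of PRP, and at the 1-, 5-, 10-, and 15-minute marks while undergoing PRP application in each eye". For the time after laser, the section mentions "conducting a 45-minute observation period after the PRP session" as part of safety monitoring, with no vital-sign reading attached to it.

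**Design.** The randomisation text under Study design gives one eye of each patient to one arm and the other eye to the alternative. The right eye is always lasered first, with 10 minutes between eyes.

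**Analysis.** The Statistical Analysis Plan states "Repeated measurements of related groups with a non-normal distribution were analyzed using the Friedman test". The following sentence assigns Mann-Whitney U to comparisons of unrelated groups. Neither test is tied to a variable or time point, and no change score is defined.

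**The concern.** The quantity in the hypotheses is (rise in peribulbar eye) minus (rise in sham eye). A Friedman test across times within one arm asks a different question: do the values move over time in that arm? A significant result in sham eyes beside a non-significant one in peribulbar eyes is easily reported as an analgesic effect, yet it does not compare the arms.

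The one between-group test named is for independent samples, whereas the two arms consist of the two eyes of the same people. An unpaired test discards the pairing that the design was built to provide.

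What is at stake is the trial's objective evidence. The introductory text presents vital signs as the objective complement to self-reported pain, and the evaluator who administers the pain scale is not masked. If the vital signs are to carry that weight, their analysis has to address the hypothesised contrast.

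**Working it through.** **Inputs.** From the documents: 44 patients, two eyes each in opposite arms, a baseline and four readings during PRP per eye, threshold 0.05. No variances, expected rises or between-eye correlations are given for vital signs, so every such value below is an assumption. The sample size of 44 cannot be reproduced, because the SAP gives neither the difference nor the SD behind it; nothing below depends on reproducing it.

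**1. Which reading of Friedman would test the hypothesis?** The SAP does not name the factor.
- Across times within an arm (the natural reading): tests time, not arm.
- Across the two arms at one time: reduces to a sign-type test of levels, not of change.
- Across all arm-by-time cells: an omnibus test that cannot isolate the difference in change.
- Across the two eyes on a change score: would be a sign test of the right contrast, but the plan defines no such score.

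**2. How often does only one arm reach significance when the true rises are equal?** With within-arm power p and independent tests, the probability is 2p(1−p).
- p = 0.2: 2 × 0.2 × 0.8 = 0.32
- p = 0.5: 2 × 0.5 × 0.5 = 0.50
- p = 0.8: 2 × 0.8 × 0.2 = 0.32

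Simulation check: 44 pairs, 2,000 runs; assumed patient SD 8, eye SD 4, reading SD 5, and the same rise at all four readings.

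| True rise, sham / peribulbar | Friedman significant in one arm only | In both arms |
|---|---|---|
| 2 / 2 | 46% | 12% |
| 3 / 3 | 40% | 51% |
| 6 / 6 | 0% | 100% |
| 10 / 5 | 1% | 99% |

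In the first row, power per arm is 0.116 + 0.458/2 = 0.345, and 2 × 0.345 × 0.655 = 0.45, against 0.46 simulated. The last row shows the opposite failure: the rise is halved, yet both arms are significant, so the pair of tests says nothing about the difference.

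**3. Would Mann-Whitney on a change score work?** In the same simulation, applied to the 15-minute value minus baseline, it rejected in 4% to 6% of runs under equal rises and in 90% for 10 versus 5; Wilcoxon signed-rank gave 89%. The near-equality is built in, because the simulated changes are uncorrelated between eyes. If changes correlate at r, the variance of the difference is 2·SD²·(1−r), whereas an unpaired test assumes 2·SD². At r = 0.5 the unpaired standard error is √2 = 1.41 times too large.

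**4. Can a significance test establish the 10% reduction?** No; it addresses only whether the difference is zero. For the paired contrast, power ≈ Φ(Δ/(SD_diff/√44) − 1.96), with Δ = 0.1 × the sham rise and SD_diff = SD·√(2(1−r)). For a sham rise of 10, SD 5 and r = 0.5: Δ = 1, SD_diff = 5, standard error 5/√44 = 0.754, and power = Φ(1.327 − 1.96) = 26%. Over assumed rises of 5, 10 or 20, SD of 5 or 10 and r of 0 or 0.5, power runs from about 4% to 76%.

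**5. Is a mixed model with only a patient effect an adequate substitute?** No. Take eye-level SD τ and reading SD σ, with four readings per eye and no baseline adjustment. The true variance of one patient's difference in eye means is 2(τ² + σ²/4). The model pools the one between-eye and six within-eye degrees of freedom: residual variance (6σ² + σ² + 4τ²)/7, giving a variance of 2/4 of that. With σ = 4 and τ = 2: true 16; model (96 + 32)/7 = 18.3, halved to 9.1; the test statistic is inflated by √(16/9.14) = 1.32, so a nominal 5% test rejects in about 14% of trials. With τ = 4: true 40, model 12.6, inflation 1.78, about 27%.

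**The case against.** The strongest reply is that the SAP does contain a between-group test. Mann-Whitney applied to change from baseline would address the contrast, and step 3 shows it performing acceptably under assumed values. This stands in part: a reader might infer that the plan is incapable of answering the hypotheses, and the documents do not support that. What they show is that no change score, time point or test-to-variable assignment is specified, and that the named test is for independent samples while the eyes are paired.

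Three further inferences are tempting and also go too far.
- **About 20 unadjusted tests.** Five signs at four times would make 20 comparisons, and 1 − 0.95^20 = 64% if independent. The SAP nowhere says that levels will be tested at each time, and only four signs have hypotheses.
- **No reading after PRP at all.** Variables and Measurements does say before and after. The defect is an unreconciled contradiction with the timed list, not a plain absence; the 15-minute reading may be what was meant.
- **Short sessions lost unequally by arm.** The introductory text credits an anesthetic with "reducing session duration, and increasing the number of laser burns applied", but that is subconjunctival lidocaine, not this trial's technique. Friedman needs complete rows and no minimum session length is stated, so unequal loss is possible; no figure shows that it occurs.

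It can also be said that the SAP lays down no rule for inferring an arm effect from discordant within-arm tests. That is true: the 32% to 50% describes the risk if results are read that way. It peaks at 50%, falls outside the 20% to 80% power range, and would change if the two eyes' tests are correlated.

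**Conclusion.** The point holds in this form: four secondary hypotheses are between-arm contrasts of change in paired eyes, and the SAP specifies no analysis of that contrast. Within-arm Friedman tests do not supply it, and an unpaired test does not suit the design. The post-procedure value must be reconciled with a schedule that lists only baseline and readings during PRP.

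The size is conditional. One-arm-only significance under equal true rises is 32% to 50% for independent tests with within-arm power of 20% to 80%. The simulated figures and the power range rest on assumed variances and rises, since the documents give none. The structural mismatch between hypothesis and test rests on the text alone. The finding concerns secondary outcomes and does not touch the primary pain score.

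**What to change.** 1. **Outcome.** For each of the four hypothesised signs, define one value per eye: the change from that eye's own pre-PRP baseline to a prespecified summary of its readings during PRP.
2. **Analysis.** Analyse the within-patient difference between eyes by Wilcoxon signed-rank, or by a paired linear model adjusted for eye order and the two baselines. Report the estimate with a 95% confidence interval, and judge the 10% claim from the estimate and interval rather than from a p-value. If a mixed model is preferred, include an eye-within-patient effect as well as a patient effect.
3. **Wording.** Reconcile the before-and-after wording with the timed list. Rewording the hypotheses to an increase during PRP needs no new data. A new end-of-laser reading may not be feasible, because the SAP already describes observed distributions, which suggests that data are in hand. For the same reason, state when the revised analysis was fixed.
4. **Supporting output.** Keep Friedman as description only. Report, by arm, how many eyes lack the later readings. A summary of whichever readings exist gives more weight to early times in short sessions, so this count is needed to interpret it.
5. **Multiplicity.** Holm across the four hypothesised signs is optional. Treat oxygen saturation as descriptive.

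The cost is some rewording of the hypotheses and SAP and a little more analysis. If Holm is adopted, individual secondary p-values become less favourable.
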